Placental dysfunction is central to many complications of pregnancy, including preeclampsia, FGR, and stillbirth.²³ Disruption of the normal tightly-regulated developmental cascade that occurs during gestation can lead to abnormal placentation, which may manifest by functional and structural alterations such as changes in blood flow and changes in placental shape, texture, and patterns of injury.²⁴ One of the major insults that impacts placental function is hypoxia, a major regulator of angiogenesis and thus placental vascular development. Chronic hypoxic stress or cycles of intermittent hypoxia during gestation result in an inadequate supply of oxygen

to the fetus. Animal models have shown that rodents exposed to intermittent hypoxia deliver growth-restricted pups,²⁵⁻²⁷ and that these pups have long-term metabolic consequences similar to those seen in humans born with FGR.^{25, 28}

	AHI<5 (n=23)	AHI>5 (n=14)	AHI>15 (n=6)	AHI>30 (n=4)
Feto-placental weight ratio	6.3±1.5	6.1±1.3	5.8±1.0	5.3±0.3

Emerging data suggest that placentas from women with SDB have markers of hypoxia and angiogenesis.^{29, 30} Our preliminary data shows that the feto-placental weight ratio, a common metric of the balance between fetal and placental growth, decreases with increasing severity of SDB (see Figure). Furthermore, we have found that women with SDB have markers of hypoxia such as chorangiosis and increased nucleated red blood cells at a 2-fold higher frequency than women without SDB. Despite the critical role of the placenta, studies investigating uteroplacental function and structure in maternal SDB are lacking. We will provide pathologic evidence that SDB induces placental hypoxia and vasculopathic inflammation, patterns of injury that are not observed in women treated with APAP, providing highly novel mechanistic insight into mechanisms by which SDB could cause poor fetal outcomes.

Measurable objectives: 1) To conduct serial fetal growth measures via ultrasound every 4 weeks from 28 weeks' gestation to 36 weeks' gestation to demonstrate that growth falls across centiles (defined as $\geq 30\%$ fall in centile in women with SDB but not in those using APAP; 2) To obtain placental tissue and perform histologic examination using a rigorous, methodical pathologic review adapted from Salafia & Popek³¹ to demonstrate that placentas of women with SDB show significantly more hypoxic injury and inflammation than placentas of women using APAP therapy.

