The first subject is truly random; for subsequent subjects the treatment allocation that minimizes the imbalance of selected factors between groups is identified and subjects are assigned to the treatment or non-treatment group, with higher probability being given to assignment to the group that results in the least imbalance between groups. This maintains randomness in the assignment with the advantage of making small groups closely similar for subject characteristics at all stages of the trial. Minimization is the only acceptable alternative to true randomization and may be superior.³⁹ We will use minimization to assign to the two study groups based on the following variables: blood pressure groups (hypertensive vs. not hypertensive), diabetes (diabetic vs. non-diabetic), BMI (normal vs. overweight/obese), education (high school or less vs. post-high school), and SDB severity ($AHI 5-14.9$ ($RDI 5-14.9$) vs. $AHI 15-29.9$ ($RDI 15$ and above)). Women with an $AHI \geq 30$ or a daytime sleepiness score ≥ 16 on the Epworth Sleepiness Scale⁴⁰ will not be randomized and will be referred for clinical APAP care. However, these women will still undergo the 3rd trimester assessments (see below).

Polysomnography and APAP: Ambulatory polysomnography will be used to determine SDB status at baseline. We have previously validated home-based polysomnography in pregnant women.³² Following the nocturnal study, data will be down-loaded and analyzed using criteria of the American Academy of Sleep Medicine.³³ Women with SDB will be randomized to APAP therapy; use of auto-titrating machines allows delivery of the lowest effective pressure without need for multiple in-laboratory re-titrations as pregnancy progresses. Women will use APAP for the remainder of their pregnancies and will be closely followed by the study team. This will include remote monitoring of adherence, a major strength of our prior work. Ambulatory polysomnography will be repeated at 32-weeks with the addition of nocturnal fetal monitoring. Any woman in the non-APAP group who

no longer has SDB in the 3rd trimester will not be included in the final analysis. In our experience it is uncommon, although not impossible, for a women with SDB early in pregnancy to no longer have SDB in the 3rd trimester. Typically the severity of SDB worsens as pregnancy progresses. Nonetheless, to ensure that all non-APAP women still have SDB in the 3rd trimester it is important to repeat the sleep study in the 3rd trimester.

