investigated as it is hypothesized that the slope for fetal growth over time will not be as steep in the third trimester, especially for women with SDB. The model will take the general form: $y_{ij} = \beta_1 + \beta_2 x_{2ij} + \beta_{3ij} + \dots + \beta_p x_{pij} + \phi_{0j} + \epsilon_{ij}$ where y_{ij} is the fetal growth measure at visit i for participant j and ϕ_{0j} is the participant specific random intercept. β_1 through β_p are the fixed effect parameters estimated by the model and ϵ_{ij} is the time varying residual. The β coefficients associated with group membership are of primary interest. In addition to the random intercept per participant, random slopes will also be investigated for inclusion into the final model. For analysis of placental histology a Chi-square goodness of fit test will first be used to test for mean differences in the binary placental histology measurements between groups and a multivariable logistic regression will be used to assess group differences while controlling for potentially confounding polysomnographic variables (e.g., oxygen saturation nadir or AHI). We expect that the presence of SDB will slow fetal growth across the third trimester (>30% fall in centiles), a phenomenon not present with use of APAP therapy. Furthermore, we expect to demonstrate decreased fetoplacental weight ratio, increased chorangiosis (hypoxia), and increased vasculopathic inflammation in SDB placentas, phenomena not observed with use of APAP therapy. These data will show that maternal SDB exerts an effect on the fetus that is at least partially reversible with APAP therapy.

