Expected results and dissemination: The societal burden, medically, emotionally, and financially, of poor pregnancy outcomes is immense. Despite multiple strategies to reduce the incidence of FGR, prematurity, and stillbirth, little improvement has been made in recent years.³³ Identification of novel targets for early intervention that will yield significant real-world benefit is crucial. The proposed research is innovative because it will target maternal sleep as a modifiable risk factor for fetal growth. This will be the first study to prospectively assess the impact of APAP therapy on fetal growth. We will demonstrate that fetal growth trajectory falls across centiles in women with SDB during pregnancy and that APAP therapy prevents poor growth. We will also provide mechanistic data via placental pathology to support that APAP therapy minimizes hypoxic injury to the placenta. Our innovative approach requires a fusion of multidisciplinary investigators from Sleep Medicine, Maternal-Fetal Medicine, and Pathology; this represents a substantive departure from current methods of fetal surveillance. Our preliminary data strongly support a timely need for the proposed study, findings from which will be disseminated at national and international conferences and in international high-impact journals. Our findings will promote a considerable new rationale for the clinical use of APAP therapy as a novel tool in obstetric practice.

Covid19 amendment March 2020:

Due to Covid19 research operations involving face-to-face interaction were suspended. Research ultrasound visits were cancelled for all women except those on active APAP therapy. We are able to continue with some of the follow ups remotely such as questionnaire administration. However, subsequently we were no longer able to have access to offices and were thus unable to mail out home sleep test devices. In order to avoid missing a critical measure central to the project, we are requesting that disposable devices be mailed to participants – directly from the manufacturer - who would otherwise miss their third trimester home sleep test. We currently have approximately 4 women who are due to have their third trimester home sleep test in the upcoming month.

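### The placental histology analysis names a one-sample goodness-of-fit test for a two-arm comparison and does not say when its AHI or oxygen-nadir covariates are measured

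*Combined protocol and SAP*

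**What the plan says.** Under Evaluation, Analytic approach, the unadjusted comparison for placental histology is described as follows: "a Chi-square goodness of fit test will first be used to test for mean differences in the binary placental histology measurements between groups". The same sentence adds a multivariable logistic regression of group differences, "controlling for potentially confounding polysomnographic variables (e.g., oxygen saturation nadir or AHI". No measurement time is given for these covariates, and no expected lesion proportions appear anywhere.

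Under Action Plan, Polysomnography and APAP, there are two sleep studies. The first precedes allocation: "Ambulatory polysomnography will be used to determine SDB status at baseline". The second follows it: "Ambulatory polysomnography will be repeated at 32-weeks with the addition of nocturnal fetal monitoring". Between the two, in the APAP arm, "Women will use APAP for the remainder of their pregnancies". The same section says that any non-APAP woman who "no longer has SDB in the 3rd trimester will not be included in the final analysis". It states no matching rule for the APAP arm.

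The placental data are meant to carry the mechanism. Under Expected results and dissemination the plan says: "We will also provide mechanistic data via placental pathology to support that APAP therapy minimizes hypoxic injury to the placenta".

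**The concern.** There are two separate defects in one sentence.

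First, a goodness-of-fit test asks whether one sample departs from proportions fixed in advance. Comparing two randomised arms on a binary lesion is a different problem, because both proportions are estimated. The phrase about mean differences should also refer to differences in proportions. An analyst who followed the wording would have to invent the expected proportions, and the obvious candidate, the control arm's observed rate, gives an invalid test.

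Second, AHI and oxygen nadir exist at two times. A baseline value is a legitimate covariate. A 32-week value is measured after randomisation, during a treatment intended to change it, and lies on the hypoxia pathway that the plan sets out to demonstrate. Adjusting for it would answer a different question from the effect of APAP on the placenta, and a real effect could be reported as absent.

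**Working it through.** **What there is to reproduce.** The plan gives no power or error figure for placental histology. Its only calculation, for birth weight (551 g difference, SD 625 g), gives 90.0% power at 27 per group by the normal approximation, as stated. It supplies the arm sizes used here, 27 and 30. Absolute lesion rates are not given. The one ratio, "increased nucleated red blood cells at a 2-fold higher frequency than women without SDB", compares SDB with no SDB, not APAP with no APAP. Lesion rates below are therefore assumptions, shown over a range.

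**Part 1: the named test.** Let *a* and *b* be lesion counts in the APAP and control arms, *n* per arm, and p̄ = (*a* + *b*)/2*n*.

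- Test of independence: X² = (*a*/*n* − *b*/*n*)² / [p̄(1 − p̄)·2/*n*].
- Goodness of fit with the control rate *q* = *b*/*n* taken as known: G = (*a* − *nq*)² / [*nq*(1 − *q*)].

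Both are referred to 3.84 (1 df, 5%). Take 6/30 against 12/30 as an example. G = (6 − 12)²/(30 × 0.4 × 0.6) = 36/7.2 = 5.0, which is significant. X² = 0.2²/(0.3 × 0.7 × 2/30) = 0.04/0.014 = 2.86, which is not. G ignores the sampling error of the control arm, so it uses half the true variance. In large samples its type I error is 2[1 − Φ(1.96/√2)] = 16.6%.

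Exact enumeration of two binomials with equal true rates gives these type I errors:

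| Lesion rate (assumed) | Independence, n=27 | Goodness of fit, n=27 | Independence, n=30 | Goodness of fit, n=30 |
|---|---|---|---|---|
| 10% | 5.2% | 22.4% | 5.4% | 20.5% |
| 20% | 5.7% | 19.0% | 4.9% | 17.7% |
| 30% | 5.5% | 18.0% | 4.9% | 16.9% |
| 40% | 4.7% | 16.9% | 4.9% | 16.9% |
| 50% | 4.2% | 16.8% | 5.2% | 16.0% |

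A different literal reading tests the lesion counts against an equal split, (*a* − *b*)²/(*a* + *b*). It errs the other way, at 0.7-3.8% over the same rates. The wording does not fix the error rate.

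**Part 2: covariate timing.** The approximate variance inflation of the arm coefficient is 1/(1 − r²), where r is the correlation between arm and covariate. All inputs are assumptions except where a source is named:

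- baseline AHI lognormal (median 10, log SD 0.6), truncated to 5-29.9, which is a simplification because women can enter on RDI alone;
- untreated 32-week AHI of 1.2 × baseline, log SD 0.4;
- non-APAP women kept only if 32-week AHI is at least 5 (a simplified form of the exclusion rule);
- 85% of the APAP arm treated (borrowed from the adherence milestone under Evaluation), with on-treatment median AHI 2.5 or 5 and log SD 0.4.

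| 32-week AHI recorded on APAP | r | Variance inflation | Standard error × |
|---|---|---|---|
| Untransformed, median 5 | −0.49 | 1.32 | √1.32 = 1.15 |
| Untransformed, median 2.5 | −0.57 | 1.48 | √1.48 = 1.22 |
| Log, median 5 | −0.63 | 1.64 | √1.64 = 1.28 |
| Log, median 2.5 | −0.75 | 2.29 | √2.29 = 1.51 |

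This loss arises with no mediation at all. As an illustration, take risks of 0.50 against 0.25 with 30 per arm. Simulated power for the arm effect is 49-52% unadjusted, 36-42% with untransformed 32-week AHI and 23-35% with log AHI. If the 32-week study is recorded off APAP, variance inflation is about 1.02 and the loss is negligible.

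Mediation adds bias. In a separate simulation APAP lowers AHI by 50% or 80% and acts on the placenta only through AHI, which is an extreme case. The APAP odds ratio is 0.55 or 0.40 unadjusted, 0.54 or 0.39 adjusted for baseline AHI, and 1.01 in both cases adjusted for post-randomisation AHI.

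**The case against.** On the test, the fair reply is that this is a slip of name. The sentence speaks of binary measures compared between groups and supplies no expected proportions, so the ordinary 2x2 chi-square test was almost certainly intended. That stands. A reader might infer that the placental comparison will run at 16-22% error. The documents do not support this, because that figure applies only if the wording is followed literally in one particular way.

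On the covariates, the text leans towards baseline. It calls them potentially confounding, which a variable changed by treatment is not. Baseline SDB severity is already a minimisation factor. The 32-week study has other stated purposes: confirming that SDB persists, and fetal monitoring. This is a good argument but not a decisive one. Confounding is often used loosely, and the Covid19 amendment treats the third-trimester sleep test as too important to lose, so an analyst would not obviously set its values aside. A reader might infer that the plan adjusts for a mediator. The text does not say so, and it does not say whether the APAP arm is recorded while using APAP.

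The size of the precision loss also depends on the scale of AHI, and the plan mentions no transformation. The log-scale figures are the pessimistic end and should not be read as the whole range.

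Finally, a reader might infer that arms this small require Fisher's exact test. The enumeration does not support that: the chi-square test holds 4.2-5.7% at lesion rates of 10-50%.

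**Conclusion.** The point holds in limited form. The named test is wrong for the comparison as written and is probably a misnaming. Its consequence under a literal reading (control rate treated as known) is a type I error of about 16-22% instead of 4.2-5.7%, at assumed lesion rates of 10-50% with 27-30 per arm.

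The missing covariate time point is a risk that the wording permits, not a demonstrated error. It does harm only if 32-week values are used and the APAP arm is recorded on APAP. In that case variance inflation is about 1.3-1.5 with untransformed AHI or 1.6-2.3 with log AHI, and any effect running through AHI or nadir is adjusted away. These sizes rest on assumed AHI distributions and mediation, for which the documents give no data.

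Confidence is high that the test is misnamed and the time point unstated, and lower for the projected loss. Only the secondary outcome is concerned. The unadjusted comparison does not depend on covariate timing, and the primary multi-level model and the sample size are untouched.

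**What to change.** In the Analytic approach paragraph:

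- Replace the goodness-of-fit wording with the 2x2 chi-square test of independence, for a difference in lesion proportions between the two randomised arms.
- State that the logistic model adjusts only for pre-specified polysomnographic values from the baseline sleep study, and name them.
- Label any model containing 32-week AHI or oxygen nadir as exploratory mediation analysis, and report with it whether those recordings were made on or off APAP.

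The cost is two or three sentences. No new data, visits or participants are needed, and no stated sample size or power figure changes. Making the change before the histology is analysed by arm removes a choice that could otherwise be made after seeing the results.

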Title: Auto-PAP Therapy For Improved Fetal Growth

Statement of issues to be addressed/target population: The target population is pregnant women with sleep-disordered breathing (SDB). SDB affects up to 35% of 3rd trimester pregnant women in the general population^{1, 2} and up to 85% of those with hypertensive pregnancies^{3, 4}. It is associated with fetal growth restriction (FGR),^{5- 7} a serious condition that affects approximately 10% of fetuses and is a significant disease burden not only for mothers but also for the long-term health of the child. *The purpose of this proposal is to prospectively demonstrate that fetal growth trajectories are altered by maternal SDB such that estimated fetal weight measures will slow across the last trimester in women with SDB, a pattern that will not be observed in women treated with APAP therapy.* Moreover, we will provide evidence that SDB induces placental hypoxia and vasculopathic inflammation, mechanisms by which SDB could cause poor fetal outcomes. Findings will demonstrate that APAP therapy, a non-invasive and non-pharmacological intervention, will have clinical utility as a novel therapy to address fetal growth problems.

Description: goals, measurable objectives, action plans, and capacity to carry out the study:

Goal: The primary goal is to provide evidence that in women with SDB fetal growth trajectory is impaired, defined as fetal weight falling across standard centile curves, but that fetal growth is not impaired in women treated with APAP therapy. In addition, we will show that placental tissue of women with SDB has evidence of hypoxia and inflammation, which will not be found in women treated with APAP therapy. These data will demonstrate that APAP therapy can minimize serious morbidity in pregnant women.

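### If a placental lesion has no cases in the APAP arm, the planned logistic regression gives no finite adjusted odds ratio and no usable Wald interval or p-value, and the plan names no fallback

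*Combined protocol and SAP*

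**What the plan says.** The Analytic approach paragraph (under Evaluation) treats the placental data as "binary placental histology measurements between groups". For the unadjusted comparison, "a Chi-square goodness of fit test will first be used". For the adjusted comparison, "a multivariable logistic regression will be used to assess group differences while controlling for potentially confounding polysomnographic variables", with oxygen saturation nadir and AHI given as examples. It does not say which test or interval is to be taken from the logistic model, and gives no rule for sparse tables.

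Two places predict the APAP-arm result in absolute terms. The Goal says that placental tissue of women with SDB "has evidence of hypoxia and inflammation, which will not be found in women treated with APAP therapy". The placental part of the Background speaks of "patterns of injury that are not observed in women treated with APAP". The Analytic approach lists a lower fetoplacental weight ratio, more chorangiosis and more vasculopathic inflammation in SDB placentas, and calls these "phenomena not observed with use of APAP therapy".

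The only information on lesion frequency is relative: in the Background, women with SDB had chorangiosis and "increased nucleated red blood cells at a 2-fold higher frequency than women without SDB". The analysed sample is to be no smaller than 27 per group (Potential Problems and Alternative Strategies), from 30 enrolled per group (Sample Size and Power Calculation).

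**The concern.** When one arm has no events and the other has at least one, the data are separated by treatment. The likelihood keeps rising as the log odds ratio for treatment goes to minus infinity, whatever other covariates are in the model. Software then either reports non-convergence or prints an arbitrary large coefficient with an enormous standard error, and the Wald p-value drifts toward 1.

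An absent lesion on APAP is what the Goal describes as success. In that case the reader would see a clear unadjusted difference beside an adjusted analysis with no odds ratio and, on Wald output, no evidence of an effect. The plan does not say how the two are to be reconciled. The Placental Pathology section covers several families of lesion, so a single uncommon one is enough to raise the problem.

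**Working it through.** **Inputs from the documents.** 27 analysed per arm (30 enrolled); binary lesions; chi-square test, then logistic regression. **Assumed, because the documents do not give them:** absolute lesion rates in each arm, and the test taken from the logistic model.

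**The plan's own figure.** The 27 per group was sized on birth weight: 2 × (1.96 + 1.28)² × (625/551)² = 27.0. Power at 27 is 90% by the normal approximation. The figure reproduces, but it says nothing about placental lesions, for which no power is stated.

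**Chance of an empty APAP cell**, (1 − p)^n:

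| Assumed APAP-arm rate | n = 27 | n = 30 |
|---|---|---|
| 1% | 76% | 74% |
| 2% | 58% | 55% |
| 5% | 25% | 22% |
| 10% | 6% | 4% |
| 15% | 1% | 0.8% |
| 20% | 0.2% | 0.1% |

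If APAP only halves a lesion (borrowing the 2-fold pilot ratio, which compares SDB with no SDB), the chance of no APAP cases with at least one control case is (1 − p_A)^27 × [1 − (1 − p_C)^27]. This is 24% for 10% vs 5%, 6% for 20% vs 10%, and 1% for 30% vs 15%.

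**A worked table: 8/27 control, 0/27 APAP.**

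- Pearson chi-square: 54 × (8 × 27)² / (27 × 27 × 8 × 46) = 9.39, p = 0.002. Fisher exact p = 0.004.
- Maximum likelihood with one simulated AHI covariate: coefficient −8.3 (SE 19) after 8 iterations, −12.3 (SE 141) after 12, −20.3 (SE about 7,700) after 20. Wald p = 0.66, then 0.93, then 0.998. It never settles.
- Likelihood-ratio test on that same model: p = 0.0004. Unadjusted, by hand: 2 × [8 ln(8/27) + 19 ln(19/27) − 8 ln(8/54) − 46 ln(46/54)] = 12.49, also p = 0.0004.
- Firth penalised fit, adjusted: odds ratio 0.042, penalised likelihood-ratio p = 0.0016. Hand check, unadjusted, where Firth amounts to adding 0.5 to each cell: the APAP odds are 0.5/27.5 = 0.0182, the control odds are 8.5/19.5 = 0.436, and their ratio is 0.042.
- Risk difference (control minus APAP): 0.296. Wilson limits are 0.159 to 0.485 for 8/27 and 0 to 0.125 for 0/27. The distance from the estimate to the lower limit for 8/27 is 0.137 and to the upper limit is 0.189, so the Newcombe limits are 0.296 minus √(0.137² plus 0.125²), which is 0.11, and 0.296 plus 0.189, which is 0.48.

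**Simulated power**, 27 per arm, treatment plus two correlated null covariates:

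| Control vs APAP rate | Wald | ML likelihood ratio | Firth | Chi-square |
|---|---|---|---|---|
| 30% vs 5% | about 41% | about 75% | about 69% | about 75% |
| 30% vs 2% | about 27% | about 91% | about 85% | about 90% |

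Under no effect, the ML likelihood-ratio test rejected in about 8% of trials for a lesion present in 10% of both arms. Firth stayed at or below 5% within simulation error.

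**The case against.** Four points on the other side carry weight.

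First, a reader might infer that the placental analysis as a whole breaks down, or loses its power, when APAP works best. The documents do not support that. The plan never specifies a Wald test, and the power loss belongs to that test: the likelihood-ratio test on the same model keeps about 75% and 91%. The chi-square test, which the plan runs first, is unaffected by the empty cell and in a randomised comparison already addresses the treatment question. This objection stands. What it leaves is the estimate: with an empty cell, no likelihood-ratio test makes the ML odds ratio finite or closes its interval at both ends. Its power advantage over Firth is also bought partly with a type I error above 5%.

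Second, a reader might infer that the plan formally assumes a zero event rate on APAP. It does not. The phrase in the Analytic approach covers a weight ratio, which cannot be absent, so it more naturally means that the change is not seen. The next sentence there speaks of partial reversal, the Measurable objectives ask only for significantly more injury without APAP, and Expected results and dissemination speaks of reduced injury. The Goal and the Background sentence are plainer, but they are statements of aim.

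Third, a 2-fold ratio suggests a modest effect. Under a halving, an empty cell is uncommon (1% to 6%) unless the untreated rate is as low as about 10%. In that rare-lesion case chi-square power is only about 8%, so no model would rescue the comparison.

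Fourth, it might be inferred that lesions without a finite fit would be dropped or reported selectively. Nothing in the documents says so.

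**Conclusion.** The point holds as a sparse-data gap in one adjusted secondary analysis. The mathematics is certain: with no cases on APAP and at least one in the control arm, the named model has no finite maximum-likelihood odds ratio, and its Wald output is meaningless. How often this happens depends on APAP-arm lesion rates that the documents do not give: at n = 27, from 58% of trials at a 2% rate to 1% at 15%. The power figures further assume particular rates, null covariates and a stated test.

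The primary fetal growth model is not affected, and a large placental difference would still be detected by the unadjusted test. What would be missing is a usable adjusted estimate and interval, with the choice of remedy left until after the data are seen. It is worth correcting because the correction is cheap.

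**What to change.** In the Analytic approach paragraph, replace the unspecified logistic regression with Firth penalised logistic regression for every binary lesion, tested by the penalised likelihood-ratio test and reported with a profile-likelihood interval. For each lesion, also report the risk difference between the assigned arms with a Newcombe interval, which exists when a cell is empty.

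The cost is one sentence and standard software, with no extra data and no change to study conduct. The downside is slight shrinkage of the odds ratio toward 1. The change does not settle whether the polysomnographic covariates are baseline or third-trimester values. If they are measured on treatment, a finite odds ratio would still not estimate the effect of assignment, so that needs its own decision.
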